10.5. Bone Marrow Examination

Bone marrow aspirate is optional at screening and bone marrow aspirate and biopsy will be mandatorily collected for all subjects at the time of the CR/CRi confirmation visit (within 12 weeks after clinical, imaging and laboratory response criteria have been met). Listings for bone marrow aspirate and biopsy (all parameters collected) will be provided by dose cohort for each treatment arm for all enrolled subjects.

Bone marrow collected for MRD assessment (MRD -, MRD + and not done) will be listed for all enrolled subjects. Frequency counts and percentages will be provided for MRD negativity by dose cohort and overall for each treatment arm for the Safety and EE populations.

10.6. ECOG Performance Status

Shift table from baseline to best post-baseline in ECOG performance status will be displayed by dose cohort and overall by treatment arm for the Safety population. A listing of ECOG grade will be provided as well.

10.7. B-symptoms Evaluation

Assessment of the presence or absence of B-symptoms will be performed at screening and on Day 1 for all cycles, at EoT and 28 days post last dose of IP. After the first 12 cycles of CC-122, in the absence of adverse events related to CC-122, and as clinically indicated, some Day 1 clinic visits and assessments may become less frequent.

B-symptoms are defined as any one or more of the following disease-related symptoms or signs:

- Unintentional weight loss $\geq 10\%$ within the previous six months.
- Significant fatigue (i.e., ECOG performance status of two or higher; cannot work or unable to perform usual activities).
- Fevers of greater than 100.5°F or 38.0°C for two or more weeks without other evidence of infection.
- Night sweats for more than one month without evidence of infection.

Summary tables for B-symptoms for weight loss, fatigue, fever and night sweats will be provided by visit, dose cohort and overall for each treatment arm using Safety population. Listing of B-symptoms will be provided to support the tables.

10.8. Physical Examination for Efficacy Analysis

Data collected from physical examination for measurable lymph node assessment, physical examination for non-measurable lymph node assessment will be listed.

11. SAFETY ANALYSIS

The purpose of this section is to define the safety parameters for the study and to summarize the safety results of the study. All summaries of safety data will be conducted using the Safety population and will be presented by treatment arm, dose cohort and overall. Safety measurements will include AEs, clinical laboratory information, vital sign measurements, cardiac laboratory assessment, 12-lead ECGs, LVEF assessments, monitoring for TLS and tumor flare, ophthalmological and pregnancy status evaluation. Individual subject listings (including coagulation tests such as Prothrombin Time, International Normalized Ratio (INR) and Partial Thromboplastin Time (PTT) assessment) will be provided to support the tables.

If an EoT measurement is conducted for those subjects who discontinue from the study, the data from the EoT visit will be included as a separate visit in the summary table. In addition, the data from the EoT visit as well as follow-up at 28 days visit will also be included in plots for parameters of individual subjects over time, unless otherwise specified.

11.1. Adverse Events

11.1.1. Summary of Adverse Events

AEs will be analyzed in terms of Treatment-Emergent Adverse Events (TEAEs) which are defined as any AEs that begin or worsen on or after the start of IP through 28 days after the last dose of IP. All AEs will be coded using the MedDRA® dictionary Version 22.0 or higher.

If a subject experiences the same AE more than once with a different toxicity grade, then the event with the highest grade will be tabulated in “by grade” tables. If a subject experiences multiple AEs under the same PT (SOC), then the subject will be counted only once for that PT (SOC). In addition, AEs with a missing intensity will be presented in the summary table as an intensity category of “Missing” and will not be imputed.

The incidence of TEAEs will be summarized by MedDRA SOC and PT. The intensity of AEs will be graded 1 to grade 5 by investigator according to the National Cancer Institute Common Terminology Criteria for Adverse Events (NCI CTCAE) Version 4.03 with the exception of tumor flare (NCI CTCAE version 3.0), tumor lysis [REDACTED] and laboratory abnormalities as recommended by the IWCLL guidelines for the diagnosis and treatment of chronic lymphocytic leukemia [REDACTED] For all other AEs, the intensity will be determined by the investigator as mild (Grade 1), moderate (Grade 2), severe (Grade 3), life-threatening (Grade 4) or death (Grade 5).

Tables summarizing the incidence of TEAEs by dose cohort will be generated for each treatment arm with the following:

- TEAEs;
- TEAEs related to CC-122, other combination drug (ibrutinib or obinutuzumab) and CC-122 and/or other combination drug;
- TEAEs of NCI CTCAE grade 3 or 4 by maximum NCI CTCAE grade;
- TEAEs related to CC-122, other combination drug (ibrutinib or obinutuzumab) and CC-122 and/or other combination drug with NCI CTCAE grade 3 or 4 by maximum NCI CTCAE grade;
- TEAEs with death outcome;

- TEAEs with death outcome related to CC-122, other combination drug (ibrutinib and obinutuzumab) and CC-122 and/or other combination drug;
- Serious TEAEs;
- Serious TEAEs related to CC-122, other combination drug (ibrutinib and obinutuzumab) and CC-122 and/or other combination drug;
- TEAEs leading to discontinuation of CC-122, of other combination drug (ibrutinib and obinutuzumab), of CC-122 or other combination drug, of CC-122 and other combination drug;
- TEAEs leading to dose reduction of CC-122, of other combination drug (ibrutinib), of CC-122 or other combination drug, of CC-122 and other combination drug;
- TEAEs leading to dose interruption of CC-122, of other combination drug (ibrutinib and obinutuzumab), of CC-122 or other combination drug, of CC-122 and other combination drug.

As well as

- TEAEs by cycle of onset;
- Febrile Neutropenia, TFR, TLS by cycle of onset and overall;
- TEAEs related to CC-122, other combination drug (ibrutinib or obinutuzumab) and CC-122 and/or other combination drug, by cycle of onset;
- TEAE with onset from second to sixth CC-122 cycle leading to dose reduction/discontinuation of CC-122, of other combination drug (ibrutinib and obinutuzumab), of CC-122 or other combination drug, of CC-122 and/or other combination drug;
- TEAE by CC-122 cycle of onset and leading to dose reduction/discontinuation of CC-122, of other combination drug (ibrutinib and obinutuzumab), of CC-122 and/or other combination drug, of CC-122;
- TEAEs by maximum NCI CTCAE grade;
- TEAEs related to CC-122, other combination drug (ibrutinib or obinutuzumab) and CC-122 and/or other combination drug, by maximum NCI CTCAE grade;
- Common ($\geq 10\%$) TEAEs;
- Common ($\geq 20\%$) TEAEs;
- Common ($\geq 10\%$) TEAEs related to CC-122, other combination drug (ibrutinib and obinutuzumab) and CC-122 and/or other combination drug;
- Common ($\geq 20\%$) TEAEs related to CC-122, other combination drug (ibrutinib and obinutuzumab) and CC-122 and/or other combination drug;
- Selected TEAE of interest by aggregated terms;
- TEAEs by PT.

Selected TEAEs/ serious AEs (SAEs) of interest as determined by the mechanism of action, known class effects, or TEAEs observed to date will be summarized by treatment arm and dose cohort, and then grade or cycle of onset. Standardized MedDRA queries (SMQs) will be used in the search strategy for some of the selected AEs of special interest, intending to aid in case identification. The groupings of selected AEs,

described by one phrase or topic term will be determined by clinicians based on SMQ or relevant search terms and provided to statistician, prior to database lock.

The selected TEAEs of interest include:

- Cardiac Failure (SMQ)
- Embolic or Thrombotic Events (SMQ) including ATE (Sub-SMQ), VTE (Sub-SMQ), and Mixed Embolic and Thrombotic Events (Sub-SMQ)
- Hemorrhage (SMQ)
- Interstitial Pneumonitis (SMQ)
- Peripheral Neuropathy (SMQ)
- Tumour lysis (SMQ)
- Febrile Neutropenia (PT)
- Tumour Flare (PT)

To facilitate clinical study report writing, a summary table of TEAEs by PTs treatment arm will also be provided.

In addition, the following listings will be provided as well:

- Listing of subjects who had treatment-emergent SAE by treatment arm, dose cohort, subject number, SOC, and PT;
- Listing of subjects who had TEAEs leading to permanent withdrawal of any study drug by treatment arm, dose cohort, subject number, SOC, and PT;
- Listings of subjects who had adverse events leading to study drug reduction or interruption
- Listing of all subjects who died.

Individual subject listing of AEs will be presented as well. In addition, a listing of overdose will be provided.

A summary table for the summary of deaths information will be presented.

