10.7. Safety Analysis

All subjects who receive at least one dose of any assigned IP will be included in the safety analyses. Adverse events, vital sign measurements, physical exam findings, clinical laboratory information, ECG interpretations, LVEF assessments, pregnancy tests for FCBP, concomitant medications and procedures will be tabulated and summarized by study phase, treatment arm, and dose level, as appropriate.

In the Dose Escalation Phase, during the 28 days following initiation of CC-122, DLTs and all available safety information will be reviewed on an ongoing basis by the investigators and sponsor and summarized at the conclusion of each dose level for each treatment arm. Treatment arms will be evaluated independently. After completion of each dosing cohort the SRC will review the summarized data to determine the next step. Dose-limiting toxicity occurrence will be summarized by treatment arm and dose level as appropriate.

Adverse events observed will be coded according to the Medical Dictionary for Regulatory Activities (MedDRA). The severity or intensity of adverse events will be graded according to the CTCAE version 4.03 unless otherwise specified.

The frequency of AEs will be tabulated by MedDRA SOC and PT. In the by-subject analysis, a subject having the same event more than once will be counted only once. Adverse events leading to discontinuation from treatment, events classified as CTCAE Grade 3 or higher, IP-related events, and serious AEs will be tabulated and listed separately. By-subject listings of all AEs, serious AEs, and their attributes will be provided.

Clinical laboratory data will be summarized. Laboratory data will be graded according to CTCAE version 4.03 criteria for select analytes unless otherwise specified. The frequencies of the worst severity grade observed during treatment will be displayed in cross-tabulations by screening status.

Vital signs, ECG data and LVEF data will be summarized by cross-tabulations presenting normal and abnormal values by number of subjects at pre- and post-IP initiation.

Graphical displays will be provided where useful in the interpretation of results.

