All AEs will be recorded by the investigator from the time the subject signs informed consent until 28 days after the last dose of IP and those SAEs made known to the investigator at any time thereafter that are suspected of being related to IP. Adverse Events and serious adverse events (SAEs) will be recorded on the AE page of the eCRF and in the subject's source documents. All SAEs must be reported to Celgene Drug Safety within 24 hours of the investigator's knowledge of the event by facsimile, or other appropriate method, using the SAE Report Form, or approved equivalent form.

Additionally, for any subject receiving obinutuzumab, the site will simultaneously send the SAE Report Form to Celgene and Hoffmann-La Roche within the same timeframe and method.

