11.5. Reporting of Serious Adverse Events

Any AE that meets any criterion for an SAE requires the completion of an SAE Report Form in addition to being recorded on the AE page/screen of the eCRF. All SAEs must be reported to Celgene Drug Safety within 24 hours of the investigator's knowledge of the event by facsimile, or other appropriate method, using the SAE Report Form, or approved equivalent form. This instruction pertains to initial SAE reports as well as any follow-up reports.

The investigator is required to ensure that the data on these forms is accurate and consistent. This requirement applies to all SAEs (regardless of relationship to IP) that occur during the study (from the time the subject signs informed consent until 28 days after the last dose of IP) or any SAE made known to the investigator at any time thereafter that are suspected of being related to IP. Serious AEs occurring prior to treatment (after signing the ICF) will be captured.

The SAE report should provide a detailed description of the SAE and include a concise summary of hospital records and other relevant documents. If a subject died and an autopsy has been performed, copies of the autopsy report and death certificate are to be sent to Celgene Drug Safety as soon as these become available. Any follow-up data should be detailed in a subsequent SAE Report Form, or approved equivalent form, and sent to Celgene Drug Safety.

Where required by local legislation, the investigator is responsible for informing the Institutional Review Board/Ethics Committee (IRB/EC) of the SAE and providing them with all relevant initial and follow-up information about the event. The investigator must keep copies of all SAE information on file including correspondence with Celgene and the IRB/EC.

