 - First dose date of IP corresponds to the earliest date any dose (of CC-122, ibrutinib, or obinutuzumab) has been initiated (i.e. a non-zero dose was administered/infused).
 - Last dose date of IP corresponds to the latest date any dose (of CC-122, ibrutinib, or obinutuzumab) has been administered/infused.
- 

Time points beyond Cycle 12 will not be displayed in the by cycle summary due to limited sample size and the allowed flexible frequency of the test/measurement. Data from all time points will be included to evaluate the “most extreme” post-baseline value.

- For subjects in Arm A who have disease progress (PD) and then are treated with Ibrutinib or Obinutuzumab, following conversions will be applied:

- In the database, the cycles after PD/arm switch will be labeled with suffix “-PD” and started from “Cycle 1 Day 1”. For summary and reporting purpose, those visits will be mapped to the cycle numbers based on their original treatment schedule. For example, if a subject switch to Arm B (CC-122 plus Ibrutinib) after Cycle 2, the next visit labeled as “Cycle 1 Day 1 - PD” will be mapped as “Cycle 3 Day 1” and summarized accordingly.
 - Efficacy data collected up to the PD/arm switch, and all safety data collected in the study will be included in the summary under Arm A (and the starting dose level of CC-122 they initially received).
 - For study treatment and exposure summaries, the data collected before the treatment switch will be summarized under “CC-122 xx mg” according to the subject’s initial CC-122 dose, the data collected after the treatment switch will be summarized under “CC-122 + Ibrutinib”, or “CC-122 + Obinutuzumab”, according to which drug the subject received.
 - Subjects who switch the treatment can report AEs which are
 - related to Ibrutinib or Obinutuzumab,
 - leading to discontinuation/reduction/interruption of Ibrutinib or Obinutuzumab.

Those TEAEs will be summarized under Arm A (and starting dose of CC-122 they initially received).

- For subjects in Arm C who are not treated with CC-122:

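### Drug-related SAEs that begin or worsen more than 28 days after the last dose must be recorded, but the SAP's TEAE definition keeps them out of the main related, serious and death-outcome tables and out of the SAE listing

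*SAP*

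**What the plan says.** **Collection.** Protocol 11.1 has the investigator record all AEs from consent to 28 days after the last dose of IP, and after that "those SAEs made known to the investigator at any time thereafter that are suspected of being related to IP". Protocol 11.5 repeats the open-ended rule for SAE reporting: "any SAE made known to the investigator at any time thereafter that are suspected of being related to IP". On where the data go, protocol 11.1 says "Adverse Events and serious adverse events (SAEs) will be recorded on the AE page of the eCRF", so these late events should be in the clinical database.

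**Protocol analysis.** Protocol 10.7 says "IP-related events, and serious AEs will be tabulated and listed separately", and adds by-subject listings of AEs and serious AEs. It gives no closing date for either.

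**SAP analysis.** SAP 11.1.1 analyses AEs as TEAEs, "defined as any AEs that begin or worsen on or after the start of IP through 28 days after the last dose of IP". It makes no exception for later related SAEs. SAP 5.1 fixes the anchor: "Last dose date of IP corresponds to the latest date any dose (of CC-122, ibrutinib, or obinutuzumab) has been administered/infused". The tables of related, serious, serious-related, death-outcome and related death-outcome events in 11.1.1 are all named as TEAE tables. The SAE listing carries the same limit: "Listing of subjects who had treatment-emergent SAE by treatment arm".

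**The concern.** The incidence and severity of adverse events is a primary endpoint (protocol 3.1). After day 28 the only AEs the protocol still requires are both serious and attributed to study drug by the investigator. These are the events that the SAP's main tables then omit. The omission can move the serious-related and fatal-related counts in one direction only, downwards, and it bears on delayed toxicity. The protocol does not treat day 28 as the end of every drug consideration: pregnancy reporting runs to 18 months after obinutuzumab (protocol 11.4.1). A reader of the study report who looks only at the table of serious related events would not know that the protocol had called for further events of that kind to be recorded.

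**Working it through.** No planned figure has to be reproduced. The check compares two time windows and then goes through the outputs.

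**Windows**
- Collection of related SAEs: consent to no upper limit (protocol 11.1, 11.5).
- TEAE: first dose of IP to last dose of any IP + 28 days, judged by onset or worsening (SAP 11.1.1, 5.1).
- Gap: related SAEs with onset or worsening on day 29 or later after the last dose of any IP.

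**Cases**
1. Onset by day 28, reported months later: a TEAE, and counted. The date of awareness plays no part.
2. Onset on day 29 or later, serious and related: recorded, but not a TEAE.
3. Arm B subject who stops CC-122 and takes the 3 further cycles of ibrutinib that protocol 4.1 allows. Assuming 28-day cycles taken in full, the window closes about 3 × 28 + 28 = 112 days after the last CC-122 dose. An SAE related to CC-122 in that interval is counted, so the gap is narrower than 28 days after CC-122 would suggest.
4. Start date wholly missing: SAP 17.4 includes the event as a TEAE, a narrow exception.

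**Where a case 2 event goes**

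| Output | Included? |
|---|---|
| Related, serious, serious-related TEAE tables (SAP 11.1.1) | No |
| Death-outcome and related death-outcome TEAE tables (SAP 11.1.1) | No |
| Treatment-emergent SAE listing (SAP 11.1.1) | No |
| Individual AE listing (SAP 11.1.1) | Yes |
| Deaths listing and deaths summary (SAP 11.1.1) | Yes if fatal; no relatedness breakdown stated |
| Survival-status listing (SAP 10) | Death shown, not its cause or relatedness |
| Selected events of interest (SAP 11.1.1) | Unclear: SAEs are named beside TEAEs without a window |
| Gender and age subgroup tables (SAP 11.1.3) | Unclear for the same reason |

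If the SAEs in 11.1.3 are not limited to treatment-emergent ones, a subgroup table could contain an event that the main serious table lacks.

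**Weight of one event**
- Cohort of 3: 1/3 = 33%.
- Cohort of 6: 1/6 = 17%.
- Arm A with 20 subjects: 1/20 = 5%.

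These use the planned sizes. Actual Safety-population denominators can be larger, because subjects not evaluable for DLT are replaced (SAP 4.4) and cohorts may be enlarged (SAP 4.1.1). In Arm A they are smaller within a starting-dose group, which is how SAP 5.2.1 summarises subjects.

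**The case against.** The best defence is that a 28-day treatment-emergent window is conventional and gives a count over a period in which every subject is actively assessed. Protocol 6.1.2 ends scheduled AE evaluation 28 days after the last dose. Later SAEs arrive only if someone tells the investigator. Mixing them into the same numerator joins two ways of ascertaining events, with unequal follow-up. That stands, and it is a reason to show late events distinguishably. It is not a reason to give them no summary.

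It can also be said that protocol 10.7 names no window, so the SAP merely supplies the operational detail. That is a possible reading. But protocol 11.1 extends collection for this one class of event, and 10.7 promises that IP-related and serious events will be tabulated and listed. A definition that drops the class from both outputs is more than detail.

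Several stronger inferences are tempting and are not supported:
- That SAEs merely learned of after day 28 are lost. The test is onset or worsening.
- That the events vanish from the report. They reach the AE listing and, if fatal, the deaths outputs.
- That the follow-up contacts every 90 days are likely to bring many such events to light. Protocol 4.1 gives their purpose as disease status and later therapy. They are usually by telephone, leave out subjects who stopped for progression, and end at progression or new therapy.
- That the SAP conceals a change. The visible text of SAP 15 does not mention it, but part of that section is blacked out, so silence cannot be shown.

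**Conclusion.** The mismatch is real and follows from the text alone: events that the protocol requires to be recorded fall outside the main related, serious, serious-related and death-outcome tables and outside the SAE listing. The effect on the primary safety endpoint is limited to related SAEs that begin or worsen after day 28. Their number cannot be obtained from the documents and may be zero, so actual understatement of toxicity is not shown, only that the tables cannot display it if it occurs. If it does occur, one event is a large share of a small cohort.

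A reader might also infer that dose selection rests on incomplete safety data. The documents do not support that. DLT, NTD and MTD use the 28-day evaluation period after CC-122 starts (SAP 4.1.1, 11.1.2), and the late-toxicity rule uses the first 6 CC-122 cycles. Neither rule depends on the TEAE tables' end date.

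The conclusion assumes that the SAE wording in 11.1.1 (selected events) and 11.1.3 follows the governing TEAE sentence, and that no blacked-out text adds an exception.

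**What to change.** Choose one of two routes before database lock.

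1. Extend the TEAE definition to include any SAE suspected of being related to IP that begins or worsens later than 28 days after the last dose. Footnote those events so that the 28-day count can still be read.
2. Keep the 28-day definition and add one table and one listing of IP-related SAEs, including fatal ones, with onset after day 28.

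The second keeps the two kinds of ascertainment apart; the first needs fewer outputs. Either closes the gap. With either, apply the same rule to the SAE listing, state whether SAE in 11.1.1 and 11.1.3 means treatment-emergent, and record the choice in SAP 15.

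The cost is a few lines of SAP text and one flag on data already collected. The drawback is that reporting after day 28 is passive and uneven between subjects, so the late events should always be shown distinguishably and not read as a rate over a common follow-up period.
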